### 8.1.2 Exclusion Criteria

General exclusion criteria (to be assessed at the beginning of the baseline period based on patient interview and medical history) \*:

- 1) Patients with an active chronic disease (or stable but treated with immunomodulatory/-suppressive therapy) of the immune system other than MS (e.g. rheumatoid arthritis, scleroderma, Crohn's disease, ulcerative colitis, etc.) or with a known immunodeficiency syndrome (AIDS, hereditary immune deficiency, drug-induced immune deficiency)
- 2) Prior treatment with any of the medications below within the specified time-frame:
  - a. glatiramer acetate, interferon-beta within 4 weeks prior to screening visit 1
  - b. dimethylfumarate, diroximel-fumarate within 4 weeks prior to screening visit 1
  - c. teriflunomide within 4 weeks prior to screening visit 1, provided accelerated elimination procedure (eg. cholestyramine) was performed and teriflunomide plasma level are below 0.02 mg/L before randomization
  - d. fingolimod, ozanimod within 12 weeks prior to screening visit 1, provided normal lymphocyte counts (see exclusion criterion No. 18)
  - e. Siponimod, ponesimod within 8 weeks prior to screening visit 1, provided normal lymphocyte counts (see exclusion criterion No. 18)
  - f. natalizumab within 12 weeks prior to screening visit 1
  - g. ocrelizumab, ofatumumab, rituximab, alemtuzumab, cladribine, mitoxantrone within 52 weeks prior to screening visit 1
  - h. plasma exchange, intravenous immunoglobulin within 8 weeks prior to screening visit 1
  - i. azathioprine, methotrexate, cyclophosphamide or any other continuous immunosuppressive therapy within 24 weeks prior to screening visit 1
  - j. any other immunosuppressive monoclonal antibody treatment within 24 weeks prior to screening visit 1
  - k. Prior autologous hematopoietic stem cell transplantation
  - l. Corticosteroid treatment for MS relapse within 4 weeks prior to screening visit 1
  - m. Patients who participated in the ETIMSred trial
- 3) History of HIV, chronic or active Hepatitis C, chronic or active Hepatitis B or Syphilis, which had not been sufficiently treated
- 4) Long-Covid19 syndrome
- 5) History of splenectomy or chronic liver disease
- 6) History of coronary artery disease, chronic heart failure, aortic stenosis
- 7) Current anticoagulation therapy
- 8) Uncontrolled grade II hypertension ( $\geq 160$  systolic and/or  $\geq 100$  diastolic blood pressure according to ISH global practice guidelines) despite treatment or without treatment
- 9) History of stroke
- 10) Pregnant female confirmed by a positive pregnancy test or breast-feeding

- 11) History of alcohol or drug abuse within the 1 year prior to screening visit 1
- 12) History of or existing malignancy within the last 5 years prior to enrollment except history of basal cell carcinoma and melanoma in situ
- 13) History of or existing relevant central nervous system disorder (other than MS)
- 14) Allergy to gadolinium-based contrast agents
- 15) Any other disease or condition, which could interfere with the participation in the study according to the study protocol, or with the ability of the patients to cooperate and comply with the study procedures.

Specific exclusion criteria (to be assessed during the baseline period):

- 16) Anemia, defined as hemoglobin levels  $\leq 12.5$  g/dl (7.25 mmol/l) for female and  $\leq 13.5$  g/dl (8.37 mmol/l) for male participants (may be repeated if 11.5-12.5 g/dl in females and 12.5-13.5 g/dl in males)
- 17) Erythrocyte count  $< 4.0 \times 10^{12}/L$  in female and  $< 4.5 \times 10^{12}/L$  in male patients (may be repeated if  $> 3.8 \times 10^{12}/L$  in female and  $> 4.3 \times 10^{12}/L$  in male)
- 18) Lymphopenia with total lymphocyte counts  $\leq 1000/\mu l$  (may be repeated if  $> 800/\mu l$ )
- 19) Positive HIV testing
- 20) Positive results of baseline period testing for serological markers for hepatitis B, C, and Syphilis indicating acute or chronic infection
- 21) Patient is not eligible for blood donation according to local regulations
- 22) Having one or more of the following laboratory results:
  - a. Estimated glomerular filtration rate (eGFR)  $< 60$  mL/min/1.73 m^2 (may be repeated if eGFR 45–59 mL/min/1.73 m^2)
  - b. ALT or AST  $> 3 \times$  upper limit of normal (ULN; may be repeated if  $3.1\text{--}4 \times$  ULN)
  - c. Total bilirubin greater than  $2 \times$  ULN (may be repeated if  $2.1\text{--}3 \times$  ULN), with the exception for patients with Gilbert's disease
  - d. Platelet count  $\leq 100 \times 10^9/L$  (may be repeated if  $80\text{--}100 \times 10^9/L$ )
  - e. Abnormalities in hepatic synthetic function tests (e.g. PT, INR, PTT, albumin) as judged by the Investigator to be clinically significant

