	
 
c. teriflunomide within 4 weeks prior to screening visit 1, provided accelerated elimination procedure (eg. cholestyramine) was performed and teriflunomide plasma level are below 0.02 mg/L before randomization
 
d. fingolimod, ozanimod within 12 weeks prior to screening visit 1, provided normal lymphocyte counts (see exclusion criterion No. 18)
 
e. siponimod, ponesimod within 8 weeks prior to screening visit 1, provided normal lymphocyte counts (see exclusion criterion No. 18)
 
f. natalizumab within 12 weeks prior to screening visit 1
 
g. ocrelizumab, ofatumumab, rituximab, alemtuzumab, cladribine, mitoxantrone within 52 weeks prior to screening visit 1
 
h. plasma exchange, intravenous immunoglobulin within 8 weeks prior to screening visit 1
 
i. azathioprine, methotrexate, cyclophosphamide or any other continuous immunosuppressive therapy within 24 weeks prior to screening visit 1
 
j. any other immunosuppressive monoclonal antibody treatment within 24 weeks prior to screening visit 1
 
k. Prior autologous hematopoietic stem cell transplantation
 
l. Corticosteroid treatment for MS relapse within 4 weeks prior to screening visit 1
 
m. Patients who participated in the ETIMSred trial
 
 
 
3. History of HIV, chronic or active Hepatitis C, chronic or active Hepatitis B or prior Syphilis, which has not been sufficiently treated
 
4. Long-Covid19 syndrome
 
5. History of splenectomy or chronic liver disease
 
6. History of coronary artery disease, chronic heart failure, aortic stenosis
 
7. Current anticoagulation therapy
 
8. Uncontrolled grade II hypertension (<math>\geq 160</math> systolic and/or <math>\geq 100</math> diastolic blood pressure; according to ISH global practice guidelines) despite treatment or without treatment
 
9. History of stroke
 
10. Pregnant female confirmed by a positive pregnancy test or breast-feeding
 
11. History of alcohol or drug abuse within the 1 year prior to screening visit 1
 
12. History of or existing malignancy within the last 5 years prior to enrollment except history of basal cell carcinoma and melanoma in situ
 
13. History of or existing relevant central nervous system disorder (other than MS)
 
14. Allergy to gadolinium-based contrast agents
 
15. Any other disease or condition, which could interfere with the participation in the study according to the study protocol, or with the ability of the patients to cooperate and comply with the study procedures
 
 
Specific exclusion criteria (to be assessed during the baseline period):
 
 
16. Anemia, defined as hemoglobin levels <math>\leq 12.5</math> g/dl (7.25 mmol/l) for female and <math>\leq 13.5</math> g/dl (8.37 mmol/l) for male participants (may be repeated if 11.5 -12.5 g/dl in females and 12.5 - 13.5 g/dl in males)
 

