 A telephone interview will be conducted 3-5 days after the second dose of the first treatment cycle has been administered.

 The exact time point of V2 is not specified as it is based on central allocation to the dose group and depending on patient recruitment. Other assessments at the study site may be performed on the day before the blood donation

 Central labs: At visit 1 serology testing (Anti-HIV-1/2, HBsAg, Anti-HBc, Anti-HCV, screening for syphilis from biochemistry blood to check patient eligibility for blood donation)

 is carried out on the following working day. If the phone consultation of the [REDACTED] coincides with the phone visit [REDACTED], the phone consultation of the [REDACTED] will be skipped.

 For Sentinel Patients, no blood donation will be performed at [REDACTED]. Only safety-related assessments will be conducted.

 Sentinel Patients are not required to attend [REDACTED] and [REDACTED], as no IMP will be administered. Instead, sites will perform telephone-based AE assessments. Optional onsite visits may be arranged upon patient request.

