### 10.1 Name and Description of the Investigational Medicinal Product and Placebo

#### 10.1.1 Qualitative and Quantitative Composition

The IMP, CLS12311, consists of autologous red blood cells (RBCs) that have been chemically coupled with [REDACTED] peptides [REDACTED]

[REDACTED] from [REDACTED] proteins [REDACTED]

[REDACTED] expressed in the brain and re-suspended in saline (150 ml). [REDACTED]

[REDACTED]

[REDACTED]

[REDACTED]

The placebo consists of (uncoupled) autologous red blood cells (RBCs) re-suspended in saline (150 ml).

A detailed description of the IMP and placebo is available in the Investigator Brochure.

RBCs for CLS12311 and placebo will be isolated from 450 - 500 ml of whole blood collected of study qualifying MS patients taken by standard blood donation procedures. The blood bag containing RBCs will be transferred to TETEC AG, Reutlingen, Germany, where CLS12311/placebo will be manufactured in compliance with Good Manufacturing Practice (GMP). A complete Certificate of Analysis (CoA) is available for each batch, including batch numbers, storage conditions, and expiry dates, ensuring full traceability.

Transport and handling protocols have been established to maintain the integrity of RBCs, CLS12311, and placebo samples during the transfer to and from TETEC AG.

Informed consent is obtained from all patients before blood collection, specifically addressing both the main study and the research use of the buffy coat. The consent form outlines that the buffy coat will be sent to Cellerys AG for exploratory research use.

Table 10-1 presents the composition of the Investigational Medicinal Product (IMP) and placebo.

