### 10.2.4 Duration of Treatment

Patients of all three dose groups will receive treatment with CLS12311 within 13 weeks from enrollment in the study. CLS12311 will be administered at [REDACTED] for sentinel patients and at [REDACTED] for all other patients. CLS12311 will be manufactured from blood donations taken in [REDACTED] for treatments in [REDACTED] and from blood donation taken in [REDACTED] for treatments given [REDACTED]. Due to organizational reasons, the study design and the manufacturing schedule, the treatments may be postponed. However, both treatments of one cycle will be administered with an [REDACTED]. The sponsor and the manufacturer of the IMP will closely coordinate with the sites and other involved parties to organize all respective study visits, ensuring the adherence to the protocol. A minimum interval of [REDACTED] between the two blood donations will be maintained.

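### Exclusion criterion 16 states the female haemoglobin limit as two different values: by the protocol's own conversion, 12.5 g/dl is 7.75 mmol/l, not the 7.25 mmol/l printed beside it

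*Protocol*

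**What the plan says.** Protocol 8.1.2, exclusion criterion 16, excludes women at or below 12.5 "g/dl (7.25 mmol/l) for female and" men at or below 13.5 "g/dl (8.37 mmol/l) for male participants". The synopsis carries the same female pair: "12.5 g/dl (7.25 mmol/l) for female and". A borderline value "may be repeated if 11.5-12.5 g/dl in females and 12.5-13.5 g/dl in males"; this band is given in g/dl only. Protocol 14.1.10 allows one such repeat and does not count it as re-screening.

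On what follows from eligibility, Protocol 10.1.1 says: "RBCs for CLS12311 and placebo will be isolated from 450 - 500 ml of whole blood collected". Patients who receive a second cycle donate twice; Protocol 10.2.4 refers to a minimum interval "between the two blood donations will be maintained". The footnotes to the schedule in Protocol 4.1 exempt the first patient of each dose group from the second donation: "For Sentinel Patients, no blood donation will be performed at" the visit concerned. That leaves two donations for the six non-sentinel patients and one for the three sentinels.

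No other section of the protocol or SAP restates or corrects the haemoglobin limit.

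**The concern.** A conversion between g/dl and mmol/l for one analyte has a single factor, whatever the sex of the patient. Criterion 16 uses two. The female limit is therefore not one threshold but two, and which of them applies depends on the unit in which the result is read.

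The criterion guards a procedure with a stated anaemia risk: Protocol 13.4.1 names clinically significant iron deficiency and anaemia as possible results of the donation. Protocol 8.1 expects mostly women. There is also a reporting consequence. SAP 5.1.3 lists exclusion criteria met by reference to the protocol, and SAP 5.1.2 gives breaches of key eligibility criteria as an example of an important deviation. For a woman between the two values, the documents cannot say whether she belongs in either output.

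**Working it through.** **Inputs** (Protocol 8.1.2, criterion 16; same figures in the synopsis): female 12.5 g/dl and 7.25 mmol/l; male 13.5 g/dl and 8.37 mmol/l; female retest band 11.5 to 12.5 g/dl.

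**Step 1, factor implied by each pair.**
- Male: 8.37 / 13.5 = 0.620 mmol/l per g/dl.
- Female: 7.25 / 12.5 = 0.580 mmol/l per g/dl.

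The factors differ, so at least one pair is wrong.

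**Step 2, which pair is out of line.** The text alone shows only that the pairs disagree: with the female factor, 13.5 × 0.580 = 7.83, and the error would simply move to the men. To decide, I assume a haemoglobin monomer mass of 16.114 to 16.125 kg/mol (not in the documents), which gives factors of 0.6206 to 0.6202.
- Male: 13.5 g/dl converts to 8.38 to 8.37 mmol/l, which reproduces the printed 8.37 to within 0.01.
- Female: 12.5 g/dl converts to 7.76 to 7.75 mmol/l, which does not reproduce 7.25.
- A tetramer mass (64.458 kg/mol, also assumed) gives 1.94 mmol/l for 12.5 g/dl and fits neither pair.

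The male pair is a consistent conversion and the female pair is not.

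**Step 3, the two female limits on one scale (factor 0.620).**
- 12.5 × 0.620 = 7.75 mmol/l.
- 7.25 / 0.620 = 11.69 g/dl (11.68 to 11.69 with the assumed monomer factors).
- Gap: 7.75 − 7.25 = 0.50 mmol/l, or 12.5 − 11.69 = 0.81 g/dl.

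**Step 4, position against the retest band.** The disputed range, 11.69 to 12.5 g/dl, lies inside the band 11.5 to 12.5 g/dl and covers 0.81 / 1.0 = 81% of its width. Under the g/dl figure a woman in that range fails unless a repeat passes. Under the mmol/l figure she passes at the first reading.

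**Step 5, what else stands in her way.**
- Criterion 17: erythrocyte count below 4.0 × 10¹²/L excludes women.
- Criterion 21: ineligibility for blood donation under local regulations excludes.
- Protocol 14.1.2 and the schedule footnotes in 4.1: local donation eligibility includes haemoglobin. No threshold is given, and the sample may come from the donation itself where local rules allow, so this check need not always precede collection.

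**The case against.** The strongest case on the other side is that this is a slip in a parenthesis with little practical reach. The g/dl figure comes first, and the retest band exists only in g/dl, so a site using that band must work in g/dl. Screening haematology goes to a central laboratory (Protocol 12.2.1.3), not to about 12 site laboratories with differing units. SAP 5.5.8 shows bilirubin reported in a conventional unit with the SI value derived, which hints at the same for haemoglobin. The trial plans nine patients, and SAP Final 2.0 was revised after the data review, so screening is very probably over.

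Most of this stands and limits the consequence. It does not settle the threshold: the reporting unit for haemoglobin is nowhere stated, and no text gives one figure precedence.

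Three stronger readings are tempting, and the documents do not support them.
- A reader might infer that the mmol/l figure admits women at about 11.7 g/dl to two donations. Not being excluded by criterion 16 is not admission: criteria 17 and 21 and the local check remain, and a second donation applies only to non-sentinel patients.
- A reader might infer that sites did enrol by unit. Nothing shows that any eligibility decision used mmol/l.
- A reader might infer that later anaemia would be wrongly blamed on the study. SAP 4.7 takes the last value before the first donation as baseline, and SAP 5.5.8 gives changes and shift tables from it, so a low starting value would be visible.

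**Conclusion.** The contradiction is confirmed. The female limit in criterion 16 has two values, 0.50 mmol/l or 0.81 g/dl apart, in both places where it is stated. This rests on the male pair's factor of 0.620, which the assumed monomer mass supports; that the two pairs disagree needs no assumption.

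The consequence is conditional. If haemoglobin is read in mmol/l, women between about 11.7 and 12.5 g/dl are not excluded by criterion 16, and criterion 17, criterion 21 and a local haemoglobin check of unstated threshold are the remaining safeguards around one donation of 450 to 500 ml, or two for a non-sentinel patient. Whether anyone was affected cannot be told from the documents; if every result was read in g/dl, nobody was. No endpoint, estimate or analysis-set definition depends on it. It still needs correcting, because it is a decision threshold in an eligibility rule and not a figure in background text.

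**What to change.** 1. The sponsor states which female limit was intended. The documents do not settle this, and the review does not choose.
2. The two units are made to agree in the synopsis and in Protocol 8.1.2. If the g/dl figure stands, its pair is 7.75 mmol/l (7.76 with factor 0.6206). If the mmol/l figure stands, its pair is about 11.7 g/dl, and the female retest band must be reconciled with it.
3. Only then is the baseline haemoglobin of enrolled women checked against the stated limit, using the value and unit reported at screening. Any mismatch is classified as important or non-important under the definitions in SAP 5.1.2, not in advance, and carried into Listing 16.2.1.5.

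Cost: one figure in two places (plus the retest band if the mmol/l limit is kept) and a review of a few records. The possible downside is a protocol deviation to report.

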## 9 SELECTION AND WITHDRAWAL OF PATIENTS

### 9.1 Informed Consent

An informed consent, written in accordance with the principles of the Declaration of Helsinki, CTR and applicable national laws of the respective country has to be obtained from all patients. The informed consent forms prepared by the sponsor and approved by the ethics committees and/or competent authorities will be provided to the study centres in the local language. Each patient will sign the Informed Consent Form (ICF) before entering the study, i.e. before any study-related activities (e.g. study-specific blood drawings, baseline assessments). The study's objectives, the procedures involved, the benefits and risks of the study, alternative treatment options and the voluntary nature of participation must be explained to each subject. Patients must be given sufficient time to consider whether they wish to participate in the study. A person designated by the Investigator may give the information, if permitted by local regulations.

A copy of the signed and dated ICF must be given to the subject, while the original signed and dated ICF will be retained with the study records.

The overall process of obtaining informed consent should be documented in the medical record by the Investigator. Should there be any amendments to the Final Protocol that may directly affect

the willingness of the patient's participation in the study e.g. a change to study procedures or when new information becomes available, the ICF must be amended to incorporate this modification and the patient's informed *re*-consent must be obtained.

For any updated Consent Forms, the medical records for each patient shall document the informed consent process and that written informed consent was obtained using the updated/revised Consent Forms for continued participation in the study.

## 9.2 Patient Identification

All patients participating in the study will be assigned a unique, study-specific, patient identification number (Patient ID) at visit 1, which will be kept throughout the study duration. The format of the patient ID is as follows: C-NN-XX, where C is the country number (starting with 1 for the first country, 2 for the second, etc.). NN is the site number (with leading zero as appropriate, starting with 01), and XX is the serial number of the patient (with leading zero as appropriate starting with 01).

Example: The patient ID of the first patient entering the Visit 1 at site 01 in country number one would be: 1-01-01.

Patients will be identified by their Patient ID to ensure data protection and confidentiality. The Investigator must maintain a list of patient names corresponding to the respective patient IDs, stored securely in compliance with both GDPR and Swiss data protection laws. The Patient ID is unique to each participant and cannot be reassigned to another individual.

## 9.3 Stopping and Discontinuation Criteria

A patient's participation in the study is considered complete when all visits according to the assessments schedule have been performed ("study completers"). Patients who do not fulfil the inclusion or qualification criteria or who fulfil any exclusion criterion will be considered "screening failures". Patients meeting the qualification criteria who leave the study prior completing all scheduled visits will be regarded as "premature discontinuations". In the event of screening failure or premature discontinuation, the reason has to be documented.

If the study as a whole or the participation of an individual trial site is prematurely terminated or suspended, the concerned Investigator(s), independent ethics committee(s) (IEC(s)) and regulatory authority(ies) will be promptly informed by the Sponsor and provided with the reasons for the termination or suspension, in compliance with CTR Article 37 and Swiss ClinO Article 38. Furthermore, the clinical trial patients at the concerned trial site(s) must be immediately informed by the respective Investigator about a premature termination of the clinical trial.

All documentation related to screening failures, premature discontinuations, and trial terminations will be securely stored and made accessible for regulatory inspection.

### 9.3.1 Discontinuation Criteria Related to the Study

The study can be terminated by the Sponsor Cellerys at any time.

The criteria for early discontinuation / termination of the clinical trial include (not exclusively):

- An unexpected, significant, or unacceptable safety risk to participants enrolled in the study.
- A decision based on recommendation from applicable boards after review of safety data. A DSMB will be implemented to assess safety to provide rationale for discontinuation of the study (section 19.1.3).
- Patients cannot be recruited in sufficient numbers.

In the decision to terminate, Cellerys will always consider participants' welfare and safety. Should early termination be necessary, participants must be seen as soon as possible as described in section 14.1.9.

The Investigator may receive additional procedures to ensure that adequate consideration is given to the protection of the participant's interests. The Investigator or Sponsor depending on local regulation will be responsible for informing IRBs/IECs of the early termination of the trial.

For every patient who prematurely discontinues the trial prior to Visit 3 (dose group 1) or Visit 4 (dose groups 2 and 3), an additional patient will be included. Every sentinel patient who discontinues the trial prior to [REDACTED] has to be replaced. In the mid dose group, safety data of the second treatment cycle should be available from at least one patient (patient 4 or 5).. Any patient with insufficient safety information may be replaced at the discretion of the Sponsor, to maintain the safety integrity of the dose escalation schedule.

For participants who choose to withdraw from the study, all data collected up to the point of withdrawal will be securely stored and analyzed per protocol.

